8.2 Discontinuation of Individual Participant(s) from Study

All participants who discontinue study treatment will remain in the study and must continue to be followed for protocol-specific follow-up procedures as outlined in the schedule of assessments [Table 3]. The only exception to this is when the participant specifically withdraws consent for any further contact with him/her or persons previously authorized by the participant to provide this information.

All participants who discontinue study treatment are to be followed for up to 12 months after their end of treatment, death or the final analysis, whichever occurs first per the schedule of assessments [Table 3].

8.3 Lost to Follow-up

Every reasonable effort is to be made to contact any participant lost to follow-up during the course of the study to complete study-related assessments, record outstanding data and retrieve IP. These contact attempts should be documented in the participant's medical record.

9 STATISTICAL CONSIDERATIONS

9.1 Statistical Hypotheses

The hypothesis for the primary efficacy endpoint for each indication and dose level are given as follows:

Phase 2 Single Agent (SS, MRCL, Ovarian)

H0: iORR is 10%, at which the treatment is deemed as unacceptable.

H1: iORR is at least 25%, at which the treatment is deemed as acceptable.

Solid tumors known to express NY-ESO-1 (melanoma, NSCLC-adenocarcinoma and squamous cell as well as ESSC)

There is no formal statistical hypothesis for this cohort.

Phase 2 Combination Therapy

SS

H0: iORR is 20%, at which the treatment is deemed as unacceptable.

H1: iORR is at least 35%, at which the treatment is deemed as acceptable.

MRCL

H0: iORR is 20%, at which the treatment is deemed as unacceptable.

H1: iORR is at least 35%, at which the treatment is deemed as acceptable.

Ovarian

H0: iORR is 5%, at which the treatment is deemed as unacceptable.

H1: iORR is at least 20%, at which the treatment is deemed as acceptable.

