Objective response rate per iRECIST (iORR), as confirmed per independent central review, is monitored using the Bayesian optimal phase 2 (BOP2) design [Zhou et al, 2017]. For R/R SS, MRCL and ovarian cancer, initially 18 participants will be enrolled in each tumor-specific expansion cohort (stage 1). If the iORR does not meet the optimal stopping boundaries (see table below), then an additional 25 participants (stage 2) may be enrolled for a total maximum sample size of 43 participants. When the total number of participants reaches the maximum sample size of 43, it may be predicted that ASP0739 is effective if the number of responses is greater than or equal to 8.

Optimized Stopping Boundaries for SS, MRCL and Ovarian Cancer	
Number of participants treated	Stop if number of responses ≤
18	2

MRCL: myxoid/round cell liposarcoma; SS: synovial sarcoma

For the melanoma/NSCLC/ESCC cohort, after a minimum of 10 participants per tumor type are enrolled, if less than approximately 6 participants for each tumor type of melanoma, NSCLC-adenocarcinoma or squamous cell carcinoma or ESCC are NY-ESO-1 positive upon analysis of the most recent tissue sample, then additional participants may be enrolled into the tumor type with less than approximately 6 NY-ESO-1 positive participants.

UNIQUE to Japan Sites:

Japanese participants will only be enrolled into the monotherapy arm of the dose expansion cohort.

Phase 2 Single Agent Dose Expansion Cohort with Japanese Safety Lead-in

After the phase 1 dose escalation cohort has been completed, the phase 2 single agent dose expansion cohort with Japanese safety lead-in will be opened. The Japanese safety lead-in will enroll 3 to 8 safety evaluable participants to confirm Japanese tolerability of the RP2D of ASP0739. Japanese participants must be managed under hospitalization for 7 days from C1D1 through C1D8 during the Japanese safety lead-in. Prior to hospital discharge, the investigator must ensure participant safety by performing medical tests and procedures listed on Day 8 of Cycle 1. During the Japanese safety lead-in, an interval of 7 days will separate study treatment initiation for the second participant from the first participant. In the absence of toxicity, additional participants may be treated without any formal stagger.

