Replacement of Participants in Japanese Safety Lead-in

Participants may be replaced in the safety lead-in if:

- The participant is discovered to have enrolled without fully satisfying the eligibility criteria.
- The participant received less than the planned dose in C1 for reasons other than a DLT.
- The participant has experienced no DLT and withdraws from the study before the end of DLT evaluation period.

The decision regarding replacement of individual participants will be made by the sponsor with discussions with the treating investigator. Participants who experience DLTs in the safety lead-in will not be replaced.

The participants experiencing a DLT will be discontinued from the study unless the participants are deriving clinical benefit from the study treatment in the opinion of the investigator; in those cases, after discussion with the sponsor, participants may be allowed to continue study treatment with ASP0739 upon resolution of the DLT event to \leq grade 1 or baseline.

A participant who meets the stopping criteria will not receive study drug at C2. Additionally, at the TEM, the aggregate safety data are reviewed if any study stopping rules below have been met:

- If a study participant develops a grade 4 DLT after receiving C1
- If a study participant develops a grade \geq 3 non-hematological AE that does not resolve to \leq grade 2 within 72 hours of onset
- Note: This event should be considered a DLT.
- If there is a delay in administration of C2 by $>$ 4 weeks, it may result in discontinuation of treatment after discussion with the sponsor.

Study enrollment and study treatment of the Japanese safety lead-in will be temporarily interrupted if any of the following events occur in a participant:

- Any death that is not related to disease progression occurring within 30 days of receiving ASP0739

- Occurrence of 2 grade \geq 4 DLTs in 2 participants
- Any grade 4 hypersensitivity reaction/anaphylaxis

Phase 2 Combination of ASP0739 + Pembrolizumab

Once safety lead-in is completed and 2 radiographic responses (iCR or iPR) are observed in the phase 2 dose expansion monotherapy cohort by local or central review, the phase 2 combination cohorts may be opened in the respective tumor type where the responses were observed.

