For R/R SS, initially 22 participants will be enrolled in an expansion cohort (stage 1). If the iORR does not meet the optimal stopping boundaries (see table below) for R/R SS, then an additional 38 participants (stage 2) may be enrolled for a total maximum sample size of 60. When the total number of participants reaches the maximum sample size of 60, it may be predicted that ASP0739 in combination with pembrolizumab is effective if the number of responses is greater than or equal to 18.

Optimized Stopping Boundaries for SS	
Number of participants treated	Stop if number of responses \leq
22	3

SS: synovial sarcoma

For R/R MRCL, initially, 22 participants will be enrolled in an expansion cohort (stage 1). If the iORR does not meet the optimal stopping boundaries (see table below) for R/R MRCL, then an additional 38 participants (stage 2) may be enrolled for a total maximum sample size of 60. When the total number of participants reaches the maximum sample size of 60, it may be predicted that ASP0739 in combination with pembrolizumab is effective if the number of responses is greater than or equal to 18.

Optimized Stopping Boundaries for MRCL	
Number of participants treated	Stop if number of responses \leq
22	3

MRCL: myxoid/round cell liposarcoma

For R/R ovarian cancer, initially, 10 participants will be enrolled in an expansion cohort (stage 1). If the iORR does not meet the optimal stopping boundaries (see table below) for R/R ovarian cancer, then an additional 19 participants (stage 2) may be enrolled for a total maximum sample size of 29. When the total number of participants reaches the maximum sample size of 29, it may be predicted that ASP0739 in combination with pembrolizumab is effective if the number of responses is greater than or equal to 4.

Optimized Stopping Boundaries for Ovarian Cancer	
Number of participants treated	Stop if number of responses \leq
10	0

If both single agent and combination therapy expansion cohorts are open for the same tumor type, participants will be randomized to either single agent or combination therapy cohorts

and the randomization ratio will be based on the number of open slots still available at each cohort.

Replacement of Participants in Phase 2 Dose Expansion

If a participant in phase 2 is not response evaluable (defined as the response analysis set [RAS]), then an additional participant may be enrolled in that cohort based on sponsor discretion.

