4.2 Scientific Rationale for Study Design

This study was designed to evaluate ASP0739 as monotherapy and in combination with pembrolizumab in selected participants with advanced solid tumors known to express the NY-ESO-1 antigen. Antitumor efficacy of ASP0739 was demonstrated in preclinical studies. In a murine metastatic cancer model, a suppression of lung metastases in mice was observed, and in a murine melanoma model, a suppression of tumor growth.

The rationale for evaluating the combination of ASP0739 and pembrolizumab is supported by preclinical data obtained from a murine melanoma model that shows superior antitumor activity of combination therapy over monotherapy. ASP0739 is an aAVC expressing NY-ESO-1. Tumor volume was suppressed in animals receiving aAVC-NY-ESO-1 treatment in combination with anti-PD1 antibody relative to aAVC-NY-ESO-1 or anti-PD1 antibody alone. This suggests additive activity of ASP0739 with checkpoint inhibitors like pembrolizumab, which are known to restore immune system tumor surveillance, while ASP0739 functions by priming and activating the immune system against NY-ESO-1 tumor cells. Therefore, combination therapy may lead to higher rates of response in cancer patients compared to monotherapy. However, the combination may also increase the frequency or severity of toxicities, and thus, a dose escalation study is the appropriate setting to confirm safety for this combination.

In this study, each participant will receive ASP0739 as single agent or in combination with pembrolizumab every 28 days. To ensure participant safety, each escalation cohort will stagger treatment initiation to 28 calendar days between the treatment initiation of the first and second participants and 14 calendar days between the second and third participants at the same dose level for all escalation cohorts (as a single agent) or the safety lead-in cohort (for combination with pembrolizumab). In the absence of toxicity, additional participants may be treated at a dose level without any formal stagger.

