5.1 Inclusion Criteria

Participant is eligible for participation in the study if all of the following apply:

1. Institutional Review Board (IRB)/Independent Ethics Committee (IEC) approved written informed consent and privacy language as per national regulations (e.g., Health Insurance Portability and Accountability Act authorization for US study sites) must be obtained from the participant or legally authorized representative prior to any study-related procedures (including withdrawal of prohibited medication, if applicable).
2. Participant is at least 18 years of age and legally an adult according to local regulation at the time of signing the ICF.
3. Phase 1 Dose Escalation only:
 - Participant has R/R solid tumor known to express NY-ESO-1 (examples are, but not limited to, gastric cancer, melanoma, ESCC, NSCLC, MRCL, SS, hepatic, SCCHN or ovarian cancer) after completing available SOC therapy or is not a candidate for SOC therapy. NY-ESO-1 expression status is not required for participant entry.
4. Safety lead-in, Phase 2 Single agent and Combination Therapy only:
 - Participant has R/R SS or MRCL disease after undergoing available SOC treatment or is not a candidate for SOC therapy (must have previously received either an anthracycline or ifosfamide containing regimen or another systemic regimen, if not a candidate for either agent).
 - Participant has not received prior checkpoint inhibitor therapy (i.e., PD-1/PD-L1 treatment naïve)
 - SS: confirmation by the presence of a translocation between SYT on the X chromosome and SSX1, SSX2 or, SSX4 on chromosome 18 (may be presented in the pathology report as t [X; 18]). If unconfirmed, enrollment into the study should be discussed with the medical monitor.

- MRCL: confirmation by the presence of the reciprocal chromosomal translocation t (12;16) (q13;p11) or t(12; 22) (q13;q12). If unconfirmed, enrollment into the study should be discussed with the medical monitor.
- Participant has R/R ovarian cancer that is:
 - platinum resistant
 - OR
 - platinum-sensitive, but the participant is not a candidate for platinum or other SOC therapy.
 - Participant has not received prior checkpoint inhibitor therapy (i.e., naïve PD-1/PD-L1 treatment patients).
- Participant has R/R solid tumor (melanoma, NSCLC-adenocarcinoma and squamous cell or ESCC) after available SOC treatment or is not a candidate for SOC therapy (single-agent only).

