6.3.1 Assignment and Allocation

Priority for enrollment will be given to the safety lead-in portion of the ASP0739 and pembrolizumab combination arm when both phase 2 single agent dose expansion and combination therapy safety lead-in are open.

If both single agent and combination therapy expansion cohorts are open for the same tumor type, participants will be randomized to either single agent or combination therapy cohorts and the randomization ratio will be based on the number of open slots still available at each cohort.

UNIQUE to Japan Sites:

Japanese participants will be only enrolled into the monotherapy arm of the dose expansion cohort.

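### Should the ovarian combination null (5%) lie below the ovarian single-agent null (10%) when the order is the opposite in synovial sarcoma and liposarcoma?

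*Protocol*

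**What the plan says.** Protocol 9.1 puts the three single-agent cohorts (SS, MRCL, ovarian) under one heading with one pair of hypotheses: "H0: iORR is 10%, at which the treatment is deemed as unacceptable", against at least 25%. The combination hypotheses are then listed tumor by tumor: 20% against 35% for SS, the same for MRCL, and for ovarian cancer "H0: iORR is 5%, at which the treatment is deemed as unacceptable", against at least 20%. SAP 3 repeats all of these.

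The decision rules are in Protocol 4.1. For single agent, 18 participants are treated first, the cohort stops at 2 or fewer responses, and at 43 "it may be predicted that ASP0739 is effective if the number of responses is greater than or equal to 8". For the ovarian combination, 10 are treated first, the cohort stops at 0 responses, and at 29 the regimen may be predicted "effective if the number of responses is greater than or equal to 4". For SS and MRCL in combination, 22 are treated first, the cohort stops at 3 or fewer, and the final cutoff is 18 of 60.

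Inclusion criterion 4 in Protocol 5.1, headed "Safety lead-in, Phase 2 Single agent and Combination Therapy only", gives one ovarian disease definition for both settings. Under Protocol 6.3.1, when both cohorts are open for a tumor type, "participants will be randomized to either single agent or combination therapy cohorts". A combination cohort opens only after "2 radiographic responses (iCR or iPR) are observed in the phase 2 dose expansion monotherapy cohort by local or central review" (Protocol 4.1). SAP 1 and note 1 to the objectives in SAP 2.1 record that the study ended early and that no combination treatment was given.

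**The concern.** Adding pembrolizumab doubles the null in two tumor types and halves it in the third. A 10% response rate in ovarian cancer is unacceptable for ASP0739 alone, yet it is twice the unacceptable rate for the two drugs together. The participants meet the same disease criterion and may be randomized between the two cohorts, and Protocol 4.2 reasons that "combination therapy may lead to higher rates of response in cancer patients compared to monotherapy". Against that background the ovarian order looks like an error or an unexplained concession.

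What would be at stake is the reading of the two ovarian verdicts side by side. A combination cohort called effective next to a single-agent cohort that is not could be taken as benefit from pembrolizumab, when it may only reflect the lower bar.

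**Working it through.** **Inputs.** Hypotheses from Protocol 9.1 and SAP 3; stage sizes, stopping boundaries and final cutoffs from Protocol 4.1; the target of one-sided 0.05 with power of about 0.80 or more from Protocol 9.2.

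**Formula.** With n1 participants in stage 1, stop at s or fewer responses, maximum N, and final cutoff r, the probability of meeting the rule at true rate p is

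P(p) = sum over x from s+1 to n1 of P(X1 = x) × P(X2 ≥ r − x),

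where X1 is Binomial(n1, p) and X2 is Binomial(N − n1, p).

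**Reproducing the ovarian combination design** (n1 = 10, s = 0, N = 29, r = 4) at p = 0.05:

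- x = 1: 0.3151 × 0.0665 = 0.0210
- x = 2: 0.0746 × 0.2453 = 0.0183
- x = 3: 0.0105 × 0.6226 = 0.0065
- x ≥ 4: 0.0010
- Sum: 0.0468

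At p = 0.20 the same sum gives 0.8011.

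**All three designs.**

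| Design | At its null | Null + 5 points | At its alternative |
|---|---|---|---|
| Ovarian combination (0/10; ≥4/29) | 0.0468 at 5% | 0.2889 at 10% | 0.8011 at 20% |
| Single agent (≤2/18; ≥8/43) | 0.0480 at 10% | 0.2583 at 15% | 0.8003 at 25% |
| SS/MRCL combination (≤3/22; ≥18/60) | 0.0417 at 20% | 0.2204 at 25% | 0.8204 at 35% |

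Each design does what Protocol 9.2 claims for its own hypotheses. The 5% is not a slip in a single figure: cutoff, stage sizes and N = 29 fit 5% against 20%, and 60 + 60 + 29 = 149 and 149 + 9 = 158 are the stated combination totals.

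**Is the ovarian bar unusually lenient relative to its null?** Lowest passing rate minus null:

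- Ovarian combination: 4/29 = 13.8%, so 13.8 − 5 = 8.8 points
- Single agent: 8/43 = 18.6%, so 18.6 − 10 = 8.6 points
- SS/MRCL combination: 18/60 = 30.0%, so 30.0 − 20 = 10.0 points

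All three pairs use a 15-point gap between null and alternative. The 0.289 at a true 10% is an ordinary point on a power curve five points above the null. It is somewhat above the 0.258 and 0.220 of the other two designs, and it is not an error rate.

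**What a reader would see.** Protocol 9.4.1 summarizes phase 2 by therapy arm and tumor type, and 9.4.2.1.1 attaches a 95% Clopper-Pearson interval to each response rate. For the troubling pair, 4/29 is 13.8% (3.9% to 31.7%) and 7/43 is 16.3% (6.8% to 30.7%). The estimates and their overlapping intervals already discourage a claim that the combination did better.

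**What aligning the nulls would do.** At 10% against 25%, the present ovarian combination rule would have type I error 0.289. Keeping N = 29 and the same stage 1, a cutoff of 6 gives 0.061 and a cutoff of 7 gives 0.021, the latter with power of only 0.603. Using the 18/43 design restores 0.048 and 0.800 at a cost of 43 − 29 = 14 more participants. Nothing in the documents shows that this would be a better benchmark.

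**The case for a change.** The best case for acting is that the order is plainly on the page, unexplained, and cheap to explain. The cohort differences that the protocol does describe are the extra combination exclusions in 5.2, the possible lower ASP0739 dose level, the two-response gate, and Japanese participants in monotherapy only. All apply to SS and MRCL as well, where the null rises. Randomization between cohorts invites comparison, and the text nowhere warns that the two ovarian bars differ. If both ovarian cohorts had the same true rate, the combination alone would pass with probability (0.5497 − 0.0480) × 0.2889 = 0.145 at 10%, and (0.7759 − 0.2583) × 0.5891 = 0.305 at 15%. Here 0.5497 and 0.7759 are the chances of at least 2 responses among 18.

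The observation that no reason is given stands. The rest is weaker:

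- A feature that applies to every tumor type can matter more in one than another, so the listed differences cannot be ruled out as reasons.
- Protocol 4.2 says only that response may be higher, arguing from a murine melanoma model, and says nothing specific to ovarian cancer.
- Single agent has one common bar and combination has tumor-specific bars; that structure can put one tumor type below the common bar and two above it.
- The 0.145 and 0.305 assume that gate responses occur at the confirmed central-review rate, whereas the gate accepts local or central reads with no stated confirmation. With a 10% endpoint rate, the chance that the cohort opens and passes is 0.5497 × 0.2889 = 0.159 if gate responses run at 10%, but 0.224 if they run at 15% and 0.260 at 20%.

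**Conclusion.** No change is called for. Neither ovarian null is shown to be wrong, and nothing requires separate fixed-rate tests to share a null. Both rules meet 0.05 and 0.80 for their own hypotheses (0.0468 and 0.8011; 0.0480 and 0.8003). What is missing is a rationale, and it is missing for every phase 2 null; the ovarian background in Protocol 2.2.2 gives survival figures and antigen expression but no response rate. Writing one down would alter no boundary, sample size, error rate or analysis.

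The possible misreading is limited by the absence of any planned test between cohorts, by the reporting of each rate with its interval, and by the tentative wording of the success rule. It also cannot arise in this study: no combination treatment was given, and SAP 1 states that central-review response data were not collected. This conclusion rests on exact two-stage binomial calculations with the futility stops treated as binding, and on the documents alone. The source of the 5% and 10% figures may lie in material that neither document reproduces.

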9.2 Sample Size Determination

ASP0739 Single Agent

A total of approximately 181 participants may be enrolled in single agent treatment.

Phase 1 Single Agent Dose Escalation:

The sample size of approximately 12 participants for the dose escalation phase is not based on a statistical power calculation. The number of participants enrolled will be dependent on the DLT incidence. The estimated number of participants, a minimum of 6 evaluable and up to 12, should provide adequate information for the dose escalation and safety objectives of the study.

Phase 2 Single Agent:

It is estimated that up to approximately 169 participants may be enrolled in the single agent arms. The iORR is monitored using the BOP2 design.

For each indication (SS, MRCL or ovarian), with assumptions mentioned in the statistical hypotheses section, the statistical power would be approximately at least 0.80 while controlling the type I error rate at 0.05 (1-sided).

The sample size of approximately 40 participants for other solid tumors known to express NY-ESO-1 is not based on statistical power calculation. A minimum of 10 participants per tumor type will be enrolled. If less than approximately 6 participants within each tumor type of melanoma, NSLCC-adenocarcinoma or squamous cell and ESCC are NY-ESO-1 positive based on analysis of the most recent tissue sample, additional participants may be added so that there are approximately 6 NY-ESO-1 positive participants.

ASP0739 Combination with Pembrolizumab:

A total of approximately 158 participants may be enrolled in combination therapy.

Combination Therapy Safety Lead-in

The sample size of approximately 6 to 9 participants for safety lead-in is not based on a statistical power calculation. The number of participants enrolled will be dependent on the DLT incidence. The estimated number of participants should provide adequate information for the safety objectives of the study.

Phase 2 Combination Therapy:

It is estimated that up to approximately 149 participants may be enrolled in the combination therapy arms. The iORR is monitored using the BOP2 design.

For each indication, with assumptions mentioned in the statistical hypotheses section, the statistical power would be approximately at least 0.80 while controlling the type I error rate at 0.05 (1-sided).

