Adult participants with synovial sarcoma (SS), myxoid/round cell liposarcoma (MRCL) or ovarian cancer R/R to SOC who have not received prior checkpoint inhibitor therapy will receive ASP0739 as single agent and in combination with pembrolizumab (after a lead-in safety evaluation).

Adult participants with R/R solid tumors known to express NY-ESO-1 (melanoma, non-small cell lung cancer [NSCLC]-adenocarcinoma and squamous cell, and esophageal squamous cell carcinoma [ESCC]) will receive ASP0739 as single agent.

Number of Participants:

A total of approximately 339 participants may be enrolled in the study.

ASP0739 Single Agent

A total of approximately 181 participants may be enrolled in single agent treatment.

Phase 1 (Dose Escalation)

Approximately 12 participants with R/R solid tumors known to express NY-ESO-1.

Phase 2

Approximately 43 participants with R/R SS, 43 participants with R/R MRCL and 43 participants with R/R ovarian cancer will be enrolled once phase 1 single agent dose escalation is completed and the recommended phase 2 dose (RP2D) is defined.

In a separate cohort, approximately 40 participants with R/R solid tumors known to express NY-ESO-1 (melanoma, NSCLC-adenocarcinoma and squamous cell and ESCC) will be enrolled for preliminary efficacy assessment.

ASP0739 Combination with Pembrolizumab

A total of approximately 158 participants may be enrolled in combination therapy.

Safety Lead-in: Enrollment will start upon completion of phase 1 single agent dose escalation and confirmation of RP2D. Approximately 6 to 9 participants with R/R SS, MRCL or ovarian cancer may be enrolled to assess the safety of combination therapy prior to enrolling the specified number of participants for efficacy evaluation in each tumor type that is opened.

Phase 2: Approximately 60 participants with R/R SS, 60 participants with R/R MRCL and 29 participants with R/R ovarian cancer may be enrolled in a same cancer type cohort where 2 local or central radiographic responses (complete response per iRECIST [iCR] or partial response per iRECIST [iPR]) were observed with single agent and the safety lead-in is completed. Groups of participants will enroll in parallel and independently in each cohort.

Study Design Overview:

This is a phase 1, open-label study of ASP0739 in participants with R/R solid tumors known to express NY-ESO-1 and a phase 2 study of single agent and combination therapy with pembrolizumab in participants with R/R SS, MRCL or ovarian cancer.

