1.2 Study Schema

[figure not shown]
Figure 1 Study Schema

Phase 1 Dose Escalation ASP0739 Single Agent

EOT: end of treatment, NY-ESO-1: New York esophageal squamous cell carcinoma 1; Q: every

[figure not shown]
Phase 2 ASP0739 Single Agent

DLT: dose limiting toxicity; EOT: end of treatment; ESCC: esophageal squamous cell carcinoma; MRCL: myxoid/round cell liposarcoma; NSCLC: non-small cell lung cancer; NY-ESO-1: New York esophageal squamous cell carcinoma 1; Q: every; RP2D: recommended phase 2 dose; SS: synovial sarcoma; ST: solid tumor

* Melanoma, NSCLC-adenocarcinoma and squamous cell lung and ESCC (10 participants in each group).

[figure not shown]
Phase 2 ASP0739 Combination Therapy

EOT: end of treatment, MRCL: myxoid/round cell liposarcoma; MTD: maximum tolerated dose; Q: every; RP2D: recommended phase 2 dose; SS: synovial sarcoma

If the RP2D is selected at the same dose level as the MTD based on the phase 1 dose escalation portion, the combination safety lead-in will start at one dose level lower than the MTD.

Figure 2 Study Design Schema

Footnotes appear on next page

CR: complete response per iRECIST; DLT: dose limiting toxicity; ESCC: esophageal squamous cell carcinoma; iRECIST: immune response evaluation criteria in solid tumors; MRCL: myxoid/round cell liposarcoma; MTD: maximum tolerated dose; NSCLC: non-small cell lung cancer; NY-ESO-1: New York esophageal squamous cell carcinoma 1; PR: partial response per iRECIST; RP2D: recommended phase 2 dose; R/R: relapsed/refractory; SS: synovial sarcoma

*Melanoma, NSCLC-adenocarcinoma and squamous cell lung and ESCC.

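### Is the phase 2 single-agent total of up to about 169 understated because it leaves out the optional NY-ESO-1 top-up?

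*Protocol*

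**What the plan says.** For phase 2 single agent, protocol section 9.2 states: "It is estimated that up to approximately 169 participants may be enrolled in the single agent arms". On the melanoma/NSCLC/ESCC cohort the same section says: "The sample size of approximately 40 participants for other solid tumors known to express NY-ESO-1 is not based on statistical power calculation". It then says "A minimum of 10 participants per tumor type will be enrolled" and, for a type with fewer than about six NY-ESO-1 positives on its most recent tissue, "additional participants may be added so that there are approximately 6 NY-ESO-1 positive participants".

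Section 4.1 places this step after the minimum of 10 per type: "then additional participants may be enrolled into the tumor type with less than approximately 6 NY-ESO-1 positive participants". A footnote to the section 1.2 schema lists melanoma, the two NSCLC histologies and ESCC with "10 participants in each group".

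The synopsis carries the sum to the whole study: "A total of approximately 339 participants may be enrolled in the study". The combination part includes a safety lead-in: "Approximately 6 to 9 participants with R/R SS, MRCL or ovarian cancer may be enrolled". SAP section 3 repeats 181, 169, 158, the 40, the minimum of 10 and the top-up. Neither document caps the top-up or says whether the totals contain it.

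**The concern.** An up-to figure reads as a ceiling. Here most components enter at their maximum: 43 for each single-agent cohort under the BOP2 design, 60, 60 and 29 for the combination cohorts, and 9 of the 6 to 9 in the safety lead-in. The melanoma/NSCLC/ESCC cohort seems to enter at its minimum of 10 per type. One floor summed with several maxima does not give an upper bound.

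The top-up also looks likely to be triggered. The phase 2 inclusion criterion for these tumors (section 5.1) does not ask for NY-ESO-1 positivity, and the literature rates in section 2.2 are well below 60%. At stake would be the credibility of the planned size, and how far this cohort's objective response rate per iRECIST (iORR), a secondary endpoint, can be read when few of the 40 may carry the target.

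**Working it through.** **The plan's own totals.** From the synopsis and section 9.2:
- Phase 2 single agent: 3 x 43 + 40 = 129 + 40 = 169.
- With 12 in dose escalation: 169 + 12 = 181.
- Combination: 60 + 60 + 29 + 9 = 158.
- Study: 181 + 158 = 339.

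All match exactly. Four groups of 10 give the 40. Three groups (NSCLC pooled) at the minimum would give 129 + 30 = 159.

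**Would the top-up condition be met?** Assume enrolled participants have the section 2.2 rates: melanoma 32% to 45%, ESCC about 32%, NSCLC 12% to 25% (not split by histology, so applied to both). The binomial probability of fewer than 6 positives in 10 is:
- melanoma 0.738 (at 45%) to 0.936 (at 32%);
- ESCC 0.936;
- each NSCLC histology 0.980 (at 25%) to 0.9996 (at 12%).

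At least three of four types fall short with probability 0.972 (upper rates) to 0.996 (lower rates). If about 6 is read as 5, this is 0.83 to 0.96.

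**Size if only known positives are added.** The expected shortfall per type is E[max(6 - X, 0)], with X the positives among the first 10. In the order melanoma, ESCC and the two NSCLC groups:
- upper rates: 1.63 + 2.82 + 3.50 + 3.50 = 11.5, so the cohort is 51.5 and the total 129 + 51.5 = 180.5;
- lower rates: 2.82 + 2.82 + 4.80 + 4.80 = 15.2, so 55.2 and 184.2.

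This is 7% to 9% above 169.

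**Size if unselected participants are added until the sixth positive.** Expected enrolment per type is about 6/p:
- upper rates: 13.3 + 18.8 + 24 + 24 = 80;
- lower rates: 18.8 + 18.8 + 50 + 50 = 138.

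The two NSCLC groups supply 48 of the 80 and 100 of the 138, from a single unsplit rate. With NSCLC as one type the cohort is about 56 to 88.

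**What the 129 assumes.** Each of the three cohorts stops at 18 participants if there are 2 or fewer responses. P(stop) is 0.734 at a true iORR of 10% and 0.135 at 25%. If all three cohorts share the rate and are independent:
- all three continue with probability 0.266^3 = 0.019, or 0.865^3 = 0.65;
- expected enrolment in the three is 3 x (18 + 25 x 0.266) = 74, or 3 x (18 + 25 x 0.865) = 119, against the 129 carried in the total.

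A top-up of known positives cannot exceed 4 x 6 = 24, while one cohort stopped at stage 1 saves 25. One stop therefore keeps the total at or below 169 + 24 - 25 = 168.

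**Effect on inference.** The single-agent rule (stop at 2 or fewer of 18, success at 8 or more of 43) has exact type I error 0.048 and power 0.800. The melanoma/NSCLC/ESCC cohort does not enter that calculation.

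**The case for a change.** The strongest case for a change is that the protocol's own rates make the condition very likely to be met, that no cap is given, and that unselected enrolment would take phase 2 single agent to 129 + 80 = 209 or 129 + 138 = 267. The word approximately cannot absorb that. One clarifying sentence would be cheap, and the SAP, written after early termination, repeats the same figures.

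The part about wording stands: 169 is not a strict ceiling, and the documents do not say whether it includes the top-up. Four groups of 10 is the natural reading, but it is an inference. Three groups of 10 plus known positives would give an expected 38.0 to 40.4, also about 40.

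The large totals do not carry the argument. They need an optional step pursued without limit in every type, unselected recruitment, one NSCLC rate for two histologies, and all three BOP2 cohorts reaching 43. The documents commit to none of these. Replacement of non-evaluable participants and tumor-specific expansion cohorts (section 4.1) also have no line in the sum, which suggests a planning estimate for the named cohorts.

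On interpretation, only about 8.8 to 12.7 of the 40 (22% to 32%) would be expected to be positive, so a split of iORR by NY-ESO-1 status would be of interest. NY-ESO-1 expression is already an exploratory biomarker, and section 9.4.5.1 allows its association with efficacy to be examined. A mandatory split would add little precision: with no responders, the upper 95% Clopper-Pearson limit is 34% for 9 positives and 25% for 13.

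**Conclusion.** No change is called for. The totals are arithmetically correct and are best read as planning figures before optional enrolment. The top-up is stated beside them, and the wording (estimated, approximately, may) does not promise a hard limit. If the option were used with known positives only, the excess over 169 would be about 11 to 15 participants, and 169 would be passed only if all three BOP2 cohorts continued to 43.

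These sizes assume that the section 2.2 rates apply to those enrolled, that NSCLC counts as two types at one common rate, and, for the stopping probabilities, that the three cohorts are independent with the same response rate.

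The cohort has no formal hypothesis (section 9.1) and its size is not power-based, so following the plan as written leaves every planned analysis sound. The study also ended early, without the combination treatment (SAP section 1), so relabelling the totals would improve the text and alter no result.
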